Appendix 5. LIST OF OTHER RA-RELATED MEDICATIONS

	GPI Codes ^	HCPCS	Prednisone Eq Dose
Weak (codeine, tramadol, combinations w/ acetaminophen/aspirin, pentazocine, meperidine, tapentadol)	65100020, 65100095,65200040,6 5100091,65100045, 6599	J2175 ,J2180 J3070 J0745	N/A

GPI codes from MediSpan.

Prednisone Eq Dose from https://globalrph.com/medcalcs/corticosteroid-converter-based-on-anti-inflammatory-potency/; http://www/nadf.us/downloads/adrenal/hormone.pdf.

Low, medium, high potency corticosteroid groups defined by anti-inflammatory activity relative to hydrocortisone/; http://www/nadf.us/downloads/adrenal/hormone.pdf.

Strong opioids = opioid oral morphine equivalate conversion factor ≥ 1 ; fentanyl classified based on patch Factory-March-2015.pdf).

(https://www.cms.gov/Medicare/Prescription-Drug-Coverage/PrescriptionDrugCovContra/Downloads/Opioid-Morphine-EQ-Conversion-Factory-March=2015.pdf).

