8.3.1. Health Care Cost and Utilization

All cost and utilization measures will be identified in the 12-month pre-index period and the 12- month post-index period. Claims occurring on the index date will be considered part of the post-index period. Baseline and follow-up costs and the change in 12-month costs from baseline to follow-up will then be examined. Cost measures will comprise the total amount paid by the health plan and patient.

• All-cause health care resource utilization- Medical resource utilization will be calculated for outpatient visits, emergency department (ED) visits, and inpatient admissions and pharmacy utilization will include all paid prescription claims.

• RA-related resource health care utilization.

- Medical resource utilization related to RA will be calculated for outpatient visits, ED visits, and inpatient admissions with an RA diagnosis in any claim position.
- RA-related treatment administrations (with and without a concurrent RA diagnosis) will also be identified by presence of HCPCS codes for ADA, ETN, other TNFI and other advanced therapy; methotrexate or other NB-DMARD; low, medium and high potency orticosteroids; NSAIDS; and strong and weak opioids (*See Appendices Appendix 1, Appendix 2, Appendix 5*).
- Pharmacy utilization will included all paid prescription claims for TOFA, ADA, ETN, another TNFI or alternative MOA; methotrexate, sulfasalazine, leflunomide, hydroxychrolorquine and other NB-DMARDs; low, medium, high potency corticosteroids; NSAIDS; and weak and strong opioids (*See Appendices Appendix 1, Appendix 2, Appendix 5*).

- Health care costs-Health care costs will be computed as the combined health plan and patient paid amounts. Costs will be calculated as total costs, pharmacy/treatment costs, and medical costs. Medical costs will be further broken down into outpatient costs, emergency room costs, and inpatient costs. Costs will be adjusted using the annual medical care component of the Consumer Price Index (CPI) to reflect inflation between 2014 (the earliest start of the pre-index period) and 2017 (the cost of claims occurring in 2018 will not be adjusted).¹⁶

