- Costs from other payers are of importance for older patients dually eligible for commercial and Medicare coverage. Payments from Medicare (and other payers) will be estimated based on coordination of benefits information obtained by the health plan in its usual course of business. This study will incorporate the amounts estimated to be paid by other payers for a total paid or allowable amount.¹⁷
- All-cause health care costs- calculated as total of medical (outpatient, inpatient and ED) visits regardless of reason and all prescription costs.
- **RA-related health care costs-** RA-related health care costs will be calculated as total medical and treatment costs related to RA.
 - RA-related medical costs will include costs for outpatient, inpatient and ED vists with an RA diagnosis in any claim position
 - For outpatient visits with an RA diagnosis and administration of an RArelated treatment (see below), the non-administration costs will be characterized as part of RA-related Medical costs and the administration costs will be part of RA-related Treatment costs below.
 - Outpatient visits without an RA diagnosis, but with administration of an RArelated treatment will not be included in the RA-related Medical costs, but will be evaluated for administration costs as part of RA-relatedTreatment costs below.

Note: given variability in capture of HCPCS codes in inpatient setting across databases, RA- related treatement costs are limited to outpatient visits only.

- RA-related treatment costs will include the cost of:
 - outpatient administration of bDMARDs, NB-DMARDs, corticosterioids, NSAIDS, and opioids based on HCPCS codes regardless of RA diagnosis on claim, AND,
 - cost of prescription fills for TOFA/ADA, ETN, other advanced therapies, NB-DMARDs, corticosterioids, NSAIDS, and opioids.

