Anxiety	300.02, 293.84, 309.21, 300.0, 300.00,	F410, F422,F423, F428, F429, F4310, F4312, F4010, F4001, F4002, F409, F4001, F4002, F4010, F408, F40218, F40240, F40241, F409, F411, F064, F930, F419, F410, F411, F418, F99, F489, F449, F444, F446, F440, F441, F4481, F449, F4489, F6811, F688,R42, R000, R002, R064, R0602, R063, R0600, R0609, R0683, R0689
Sleep disorders		F519, F5102, F5109, F5101, F5103, F5109, F5119, F5111, F5112, F5119, F518, F513, F518, G479, G4730, G4700, G4730, G4710, G4720, G478, G4730, F518, G478, R0681, Z72820
Interstitial lung disease	516.9	J84.9

	GPI Codes ^	HCPCS	Prednisone Eq Dose
SYSTEMIC GLUCOCORTIC	OIDS		
High Potency			
betamethasone	22100010	J7624	0.60
dexamethasone	22100020	J1094, J1095, J1100, J8540, Q0137, Q0138, S0173	0.75
Medium Potency			
Fludrocortisone	2220003010		n/a
methylprednisolone	22100030	J1020, J1030, J1040, J2920, J2930, J7509	4
prednisolone	22100045	J1680, J2640, J2650, J7510	5
prednisone	22100040	J1690, J7506, K0125	5
Triamcinolone	22100050	J3300, J3301, J3302, J3303	4
Low Potency			
Cortisone	22100015	J0810	25
Hydrocortisone	22100025		20
NSAIDs/Salicylates	6610, 66998, 6410	J1885, J1130, J0131, C9283, J1741, C9279	N/A
Opioids			N/A
Strong (morphine, methadone, fentanyl, hydromorphone, oxymorphone, oxycodone, hydrocodone, buprenorphine, butrophanol, nalbuphine, levorphanol)	65100055,655100050, 65100025,65100035,6 5100080,6500075,651 00030,65200010,6520 0020,65200030,65100 040	J2275 ,Q9974 S0093 , J1230 ,S0109 J1170 S0092 J2410	N/A

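### Appendix 5 contradicts itself on opioid strength: acetaminophen/aspirin combinations of strong-listed opioids are strong by its footnote and weak by its list

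*Combined protocol and SAP*

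**What the plan says.** The opioid part of the medication table in Appendix 5 has two rows and a footnote.

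- **Strong row:** "Strong (morphine, methadone, fentanyl, hydromorphone, oxymorphone, oxycodone, hydrocodone, buprenorphine, butrophanol, nalbuphine, levorphanol". It names single ingredients and does not mention combination products.
- **Weak row:** "Weak (codeine, tramadol, combinations w/ acetaminophen/aspirin, pentazocine, meperidine, tapentadol". Its code list ends "5100091,65100045, 6599".
- **Footnote:** "Strong opioids = opioid oral morphine equivalate conversion factor ≥ 1", followed by a remark on how fentanyl is classified and a link to a table of conversion factors.

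Section 8.3.1 uses the two strata. RA-related pharmacy utilization ends its list of drug groups with "NSAIDS; and weak and strong opioids", and RA-related administrations name both strengths as well. RA-related treatment cost in the same section does not split them: it takes prescription fills for "NB-DMARDs, corticosterioids, NSAIDS, and opioids" as groups.

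Section 8.7.2.3 presents the utilization measures as flags and 12-month counts for baseline and follow-up, with the change between them. Section 8.7.3 provides bivariate tests by cohort.

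**The concern.** The footnote makes strength a property of the opioid. Adding acetaminophen or aspirin does not change which opioid was dispensed, so a combination should fall in the same stratum as its opioid ingredient. The weak row instead assigns combinations by product form.

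If the list is programmed as it stands, a patient who moves from an oxycodone combination to oxycodone alone would appear to step up from weak to strong, and the reverse move would appear as a step down. The rows would be read as a measure of opioid strength but would partly reflect formulation. That matters for the pre/post change and the cohort comparison wherever the mix of combination and single-ingredient products changes over time or differs between cohorts.

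**Working it through.** The plan states no figure on this point, so the check is one of consistency.

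**1. Names against codes.** Line-break spaces inside the codes were removed before counting.

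| Row | Entries | GPI codes | Codes starting 6599 |
|---|---|---|---|
| Strong | 11 | 11 | 0 |
| Weak | 6 | 6 | 1 (6599 itself) |

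No code appears in both rows. The weak row has five named single drugs and five 8-digit codes. That leaves 6 − 5 = 1 entry, the combinations, and 6 − 5 = 1 code, 6599. The match is by elimination rather than by order, since the combinations entry is third and 6599 comes last. Two strong-row codes have irregular lengths (9 and 7 digits). They may be typing or extraction errors, and nothing here rests on them.

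**2. The footnote rule applied to the strong row.** Oxycodone and hydrocodone are listed as strong. By the plan's own rule, their conversion factor is therefore at least 1. No outside table is needed for this step.

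**3. The same rule applied to combinations.** The rule has no visible exception for combination products. A combination containing oxycodone or hydrocodone is strong by the rule. The weak row's combinations entry is not limited to any opioid, so the same product is weak by the list. The strong row has no combinations entry to claim it.

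**4. Illustration with hypothetical patients.** Take 12 fills in follow-up, with the same oxycodone dose throughout.

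| Product | By footnote | By list |
|---|---|---|
| Oxycodone alone | 12 strong, 0 weak | 12 strong, 0 weak |
| Oxycodone with acetaminophen | 12 strong, 0 weak | 0 strong, 12 weak |

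The total is 12 in every cell, so only the split moves.

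**5. Size.** Let c be the share of oxycodone and hydrocodone fills that are combinations. If all of them are coded weak, strong fills of these two drugs are undercounted by the fraction c: 25% at c = 0.25 and 75% at c = 0.75. This restates the assumption and is not a result. The documents give no value for c.

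**6. Reach.** Treatment cost pools opioids. Persistence (Section 8.3) depends on the index medication. The six effectiveness criteria use adherence, dose, switching, added NB-DMARDs and glucocorticoids, but not opioids.

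**The case against.** The best defence is that the combinations entry directly follows codeine and tramadol and was meant for combinations of those drugs. Row and footnote would then agree. But neither the wording nor the prefix carries that limit, and on this reading combinations of strong-listed opioids would have no entry at all. The list would still need an edit.

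A second defence is that the text after the footnote's rule is broken in the available copy, so an exception for combinations could have been lost. The rule itself is intact and no exception is visible. If one was intended, it has to be stated.

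Third, a four-digit prefix is not suspicious in itself: the same appendix uses 6610 and 6410 for NSAIDs and salicylates. That is right. The code only supports the point, which rests on the unqualified wording.

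A further objection stands in full. The contents of 6599 and the conversion factors lie in cited sources that the documents do not reproduce. A reader might infer that oxycodone and hydrocodone combinations are demonstrably being counted in the wrong stratum, or that particular codes under 6599 should be moved. The documents do not show what the prefix retrieves, so they prove a conflict between rule and list and not an actual count of misplaced fills.

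It also stands that one list serves all cohorts and both periods. A contrast is distorted only if the product mix differs or changes, and nothing in the documents says that it does.

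**Conclusion.** Wrong as written, low severity. The footnote and the weak row give opposite answers for any acetaminophen or aspirin combination that contains a strong-listed opioid. This rests on the plan's own listing of oxycodone and hydrocodone as strong and on the absence of any visible exception for combinations.

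The size cannot be computed from the documents. The practical effect also assumes that the two strata are reported separately, as Section 8.3.1 suggests; the draft tables are in a workbook that is not part of the documents.

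A reader might carry the point over to costs, the primary outcome or the adjusted models. The first two do not use the split. Section 8.7.4 lets Section 8.3 variables be considered as predictors but does not name opioid strength among them.

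**What to change.** Classify each combination product by its opioid ingredient under the footnote rule. Replace the blanket 6599 entry with ingredient-level codes from MediSpan, which the plan already cites for its GPI codes. Combinations of strong-listed ingredients then go to strong, and only combinations of weak-listed ingredients stay weak. Reword the weak row to match, and run the strong and weak opioid utilization rows on the revised list.

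The cost is a small amount of code-list work, because the ingredient-level codes are not in the appendix and must be looked up. No other analysis needs to change.
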